3.5 Missing data and loss to follow-up

Values of the primary study endpoint (treatment success at six months) cannot be analyzed when the individual is lost to follow-up. We distinguish information which is missing because of possible progression of the underlying condition we wish to treat from information which is lost for some other reason. Earlier, we discussed methods for handling missing values for specific

uveitis fields in individuals. The discussion in this section applies only to loss to follow-up or to dropping out of the study. As emphasized in Carpenter & Kenward (2007), “there can be no universal analysis when data are missing”. Our purpose is to vary the assumptions as well as the methods, to establish that the estimates of the treatment effect are robust as such assumptions are varied.

Our priority is the preservation of the intent to treat principle. We propose to report the results from all of the following methods:

1. The use of regression-based multiple imputation, based on all observed data for the patient.
2. Use of longitudinal generalized linear mixed effects regression, with visit as a covariate, and including a random effect for each person and for each eye within each person, using all the available measurements on each individual
3. Sensitivity analysis in which missing final outcome values are assigned success or failure, and the analysis conducted conditional on these assignments.
4. Analysis of complete cases only (individuals for which the six month follow-up is available)

However, we are proposing that **method 4 (complete case analysis) be considered the primary outcome**, based on recommendation by the DSMB. All other analyses are to be considered supplementary.

Multiple imputation will be conducted as follows. The following information will be used as regression covariates: (i) age, (ii) gender, (iii) inflammation assessments at all prior time points (anterior cells, vitreous haze, and retinal/choroidal lesions), (iv) steroid dose, (v) anatomic location (by patient, classified as anterior/intermediate or posterior/panuveitis), (vi) anatomic location by history, (vii) maximum steroid dose within the 90 days prior to enrollment, (viii) steroid dose at enrollment prior to randomization or study-related intervention, (ix) country, and (x) site within country. Any additional covariates must be prespecified. A regression model for the missing outcome information will be derived; specifically, a cross-validated procedure to yield the best prediction based on complete subjects will be derived, and ten multiple imputations will be derived from it. The formula in Little and Rubin²⁵ will be used to derive the overall test statistic. All replications will be recorded and reported.

An alternative method (which we propose to use for sensitivity analysis) is hot deck multiple imputation (with ten replications).²⁵ Note that treatment assignment would never be missing. For definiteness, we choose the recursive random partitioning hot deck method used in the R package `rrp` with the default settings (command `rrp.impute`).

The possibility of data-driven modeling may render multiple imputation of an outcome variable undesirable to many reviewers as a primary outcome. An alternative method is to model the treatment success of person i at visit j , Y_{ij} , using generalized linear mixed models, with covariates being site, country, treatment assignment, country-assignment interaction, visit (1:6), and visit-drug interaction (method 2 above). Note that additional statistical modeling will be reported, in which we (a) omit visit-drug interaction, and/or country assignment interaction, (b) add visit-country interaction, or (c) add age or gender as covariates.

We believe carrying forward last observations to be particularly unhelpful in this study, because all patients are on a prescribed steroid taper. We also believe that differential loss to follow-up of well performing patients on one drug or the other could falsely make the poorer drug appear to give more favorable results, so that the complete case analysis must be interpreted with caution.

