2.1. Design summary

Study type

- Randomized, observer-masked comparative effectiveness trial
- Block randomization by site: [REDACTED]
- Sample size: 216 patients, 108 patients per arm (Table 1)

Treatment arms

- Oral methotrexate
- Oral mycophenolate mofetil

Treatment timeline

- Phase I
 - Initial treatment from 0-6 months. If treatment success (i.e. achieving corticosteroid-sparing control of inflammation at 6 months), treatment extended to 12 months.
- Phase II
 - Second therapy initiated after failure to achieve corticosteroid-sparing control of inflammation in Phase I (0-6 months).

Outcomes

- **Primary outcome (Specific Aim 1):**
 - Proportion of overall treatment success at 6 months, where treatment success is defined as controlled ocular inflammation (Table 2) with 7.5 mg/day of oral prednisone and ≤ 2 drops/day of topical 1% prednisolone acetate
- **Secondary outcomes**
 - Proportion of corticosteroid-sparing treatment success at 6 months after switching treatments in patients who are a treatment failure in the first 6 months where treatment success is defined as in Aim 1 (**Specific Aim 2**)
 - Time to control of inflammation
 - Time to treatment success
 - Proportion achieving treatment success at 5 months and sustaining, for at least 28 days, to 6 months
 - Proportion achieving treatment success at 12 months in Phase I
 - Phase I treatment success (6-12 months) with complete discontinuation of corticosteroid
 - Proportion achieving treatment success at 6 months in Phase II
 - Change in best spectacle-corrected visual acuity (BSCVA)
 - Presence of macular edema
 - Change in macular thickness
 - Change in vitreous haze as assessed clinically by the Miami (formerly Davis) scale
 - Change in vitreous haze as assessed by fundus photography grading by NEI and Miami (formerly Davis) scales
 - Efficacy for intermediate, posterior and panuveitis subgroups
 - Efficacy for retinal vasculitis
 - Proportion discontinuing due to intolerability
 - Rate of adverse events
 - Proportion discontinuing due to serious adverse events
 - Quality of life (Health related and vision related)

- Dose reduction
- Efficacy of treatment in patients with Vogt-Koyanagi-Harada (VKH) disease
- Proportion of patients beginning with at least 2+ inflammation in anterior chamber cells who experience a 2-step reduction (i.e. decreasing from 2+ to 0.5+; 3+ to 1+; 4+ to 2+).

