The primary analysis is a logistic regression with treatment arm as a predictor. For the primary analysis, we propose to use study site as a *random effect* (random intercept model). The null hypothesis is that the regression coefficient for treatment arm equals zero, which will be tested using a likelihood ratio test with one degree of freedom. We will also fit the following models: (a) a model including drug, site, and drug \times site interaction, (b) a model including only drug and site, (c) a model including only drug and country, and (d) a model with drug, country, drug-country interaction, and site within country. Countries or sites with fewer than three observations will be pooled together. Provided there is no evidence of treatment \times site interaction or treatment \times country interaction, we will report pooled treatment effects and confidence intervals. In the event evidence suggests a difference between treatment sites, we will report treatment effects by site, and repeat the analysis excluding particular sites. Similarly, evidence of a treatment \times country interaction will lead us to report treatment effects and confidence intervals by country.

Simulations suggest that use of a model containing interaction terms between site or country and treatment for the primary analysis is undesirable. Such a procedure results in modest loss of power unless the treatment effect is of opposite sign in different sites or countries.

The hypothesis test is to be two-sided with alpha of 0.05. We propose to compute the P-value by permutation testing, based on the block randomization scheme.

Prespecified Subgroup Analysis.

The prespecified subgroup analysis will test the hypothesis that there is a treatment effect separately in each anatomic group, using a logistic regression model.

We denote the two anatomic groups by X_i^3 , which equals 0 when the patient is in the intermediate group and 1 when the patient is in the posterior/pan group. In the intermediate subgroup, we plan to determine whether there is evidence of a treatment effect (regardless of the effect in the posterior/pan group). Specifically, we will conduct this analysis in two ways: anatomical site at enrollment (split into three categories: anterior, anterior/intermediate or intermediate only, and posterior/panuveitis), and anatomical location by history (split into two

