3.4 Sample Size Evaluation

3.4.1 Primary Calculation

The sample size for the trial will be 216 subjects, which we anticipate will provide approximately 80% power to detect a difference of 20% in the proportion of patients achieving control of inflammation at six months between the methotrexate and mycophenolate mofetil groups.

This sample size was determined based on the primary objective (superiority comparison of mycophenolate mofetil to methotrexate) and primary endpoint (treatment success). We assumed an effect size of 20%, as this was deemed to be clinically meaningful, and well within the distribution of the investigators' prior beliefs from published retrospective studies.

An approximate sample size is provided by the formula

$$2N = \frac{4(Z_{\alpha} + Z_{\beta})^2 \bar{p}(1-\bar{p})}{(p_c - p_i)^2} \quad (5)$$

(see Friedman et al. 2010), where α is the significance level (0.05, two sided), β is one minus the power (the desired power is 80%), p_c is in this case the probability of success in the methotrexate group (we estimate this at 0.4), p_i is the probability of success in the mycophenolate mofetil group (we estimate this at 0.6), and \bar{p} is $\frac{1}{2}(p_i+p_c)$. We assume 10% will be lost to follow-up in the first six months; details are given in the full proposal. This yields approximately 108 patients in each of the two groups, for a total of $2 \times 108 = 216$ subjects.

A power table is provided below as a sensitivity analysis (to show how the detectable effect size changes with varying success rates).

Success rate with Drug A	80% Power		90% Power	
	Detectable effect size	Success rate with Drug B	Detectable effect size	Success rate with Drug B
20%	18%	38%	21%	41%
30%	20%	50%	23%	53%
40%	20%	60%	23%	63%
50%	20%	70%	22%	72%
60%	19%	79%	21%	81%

Simulation confirms that this method yields adequate sample sizes for the logistic regression (results not shown).

Note that for the final analysis, the critical value will be adjusted slightly because of the interim analysis.

Sample size readjustment

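### The regression-based multiple imputation in SAP 3.5 omits treatment arm, so this supplementary analysis is pulled toward no difference by up to a tenth of the effect at planned loss

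*Combined protocol and SAP*

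**What the plan says.** SAP 3.5 reports four approaches to missing outcomes and makes the complete-case analysis primary, on the monitoring board's recommendation. The other three are supplementary. The first of them is regression-based multiple imputation, which a one-line summary describes as using everything observed on the patient.

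The detailed instructions later in 3.5 are narrower. They begin "The following information will be used as regression covariates: (i) age, (ii) gender, (iii) inflammation assessments at all prior time points" and continue with steroid dose, anatomic location (two items), two pre-randomization steroid doses, country, and site within country. Treatment assignment is not on the list. The list is followed by "Any additional covariates must be prespecified". One prediction model is then built by cross-validation on patients with complete data, and ten imputations are drawn from it. Nothing says that the model is fitted by arm.

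Treatment assignment appears twice nearby. The hot-deck paragraph remarks that it is never missing. The mixed-model alternative (method 2) names it as a covariate, together with a visit-by-drug interaction.

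The primary analysis in SAP 3.2.2 is a logistic regression of six-month success on treatment arm, with site as a random effect.

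**The concern.** An imputation model should contain every variable in the analysis model, and above all the one whose effect is being estimated. If arm is left out, a missing patient on mycophenolate mofetil and a missing patient on methotrexate with the same covariates receive the same predicted chance of success. The imputed part of the data then shows only as much drug effect as the covariates pass on, and the overall difference is diluted.

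What is at stake is how the sensitivity analysis is read. SAP 3.5 says the several methods are there to show whether the treatment effect holds as assumptions vary, and it warns that unequal loss of well-performing patients could mislead the complete-case result. A smaller imputed difference could be taken as a sign that the primary result is fragile, when part of the shrinkage comes from the imputation recipe.

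**Working it through.** **Inputs from the documents.** Success of 0.40 on methotrexate and 0.60 on mycophenolate mofetil, so d = 0.20 (SAP 3.4.1). Loss: "We assume 10% will be lost to follow-up in the first six months". Size: "216 patients, 108 patients per arm" (protocol 2.1). Test: "The hypothesis test is to be two-sided with alpha of 0.05" (SAP 3.2.2). Target: "approximately 80% power to detect a difference of 20% in the proportion of patients" (SAP 3.4.1). Ten imputations (SAP 3.5).

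**The plan's own figure.** SAP equation (5) gives 2N = 4 × (1.960 + 0.842)² × 0.5 × 0.5 / 0.20² = 196.2. Divided by 0.9 this is 218.0, or 109 per arm. The form with separate null and alternative variances gives (1.960√0.50 + 0.842√0.48)² / 0.04 = 96.9, rounded up to 97 per arm. Then 97 / 0.9 = 107.8, rounded up to 108 per arm and 216 in total. Power with 97 completers per arm is 0.80. The planning figures reproduce.

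**Size of the pull.** Let m be the missing fraction, equal in both arms, and r the share of the arm effect carried by the listed covariates. Observed patients show the full difference d and imputed patients show r × d:

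expected difference = (1 − m)d + m·r·d = d × [1 − m(1 − r)]

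The documents do not give r, so it is varied. The 10% column is the plan's own loss; the other columns are assumptions.

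| r | 5% missing | 10% missing | 15% missing | 20% missing |
|---|---|---|---|---|
| 0 | 0.190 | 0.180 | 0.170 | 0.160 |
| 0.25 | 0.1925 | 0.185 | 0.1775 | 0.170 |
| 0.50 | 0.195 | 0.190 | 0.185 | 0.180 |
| 0.75 | 0.1975 | 0.195 | 0.1925 | 0.190 |

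Unequal loss changes little. Take 5% missing on methotrexate, 15% on mycophenolate mofetil and r = 0. The pooled completer rate is (0.40 × 0.95 + 0.60 × 0.85) / 1.80 = 0.494. The difference is (0.51 + 0.494 × 0.15) − (0.38 + 0.494 × 0.05) = 0.179. Swapping the two loss rates gives the same 0.179.

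**Simulation check.** 3,000 trials per setting, 108 per arm, 10% missing at random, one covariate standing in for the list, logistic imputation, ten imputations, Rubin's rules, and a Wald test on the risk difference. The covariate's shift between arms is an assumption.

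| Covariate | Arm omitted: difference, power | Arm included: difference, power | Complete-case difference, same trials as arm omitted |
|---|---|---|---|
| No arm information | 0.1805, 0.743 | 0.2005, 0.807 | 0.2005 |
| Partial (shift 0.4 SD) | 0.1895, 0.785 | 0.1992, 0.803 | 0.2014 |
| Strong (shift 0.7 SD) | 0.1952, 0.824 | 0.2018, 0.823 | 0.1968 |

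The first row matches the formula at r = 0. Comparing arm-omitted with complete-case results in the same trials removes most of the simulation noise. The shortfalls are 0.0200, 0.0119 and 0.0016. Dividing each by m·d = 0.02 gives 1 − r of 1.00, 0.60 and 0.08. Part of the strong row's gap from 0.20 is therefore chance, and 0.195 is better read as the formula value at r = 0.75. With arm included, the difference returns to 0.199 to 0.202.

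**The case against.** The strongest reply is that the text need not be read as shutting arm out. The ten items are what will be used, not expressly all that may be used. The rule on additions is a condition, not a bar. The summary line is broad enough to cover treatment, and the hot-deck remark shows that the authors had it in mind. Some of this stands: the two descriptions in 3.5 differ in breadth and should be reconciled. But the detailed instructions are what an analyst would program. Nothing prespecifies arm for them, and the same section names treatment where it is meant to enter, in method 2.

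A second reply is that the covariates already carry the drug effect. Inflammation at all earlier visits and, if it means follow-up dose, steroid dose are main components of the success definition in protocol 2.5.1. That makes the bias partial, and probably small for patients lost late. It gives little protection for patients lost early, who have few post-baseline scores.

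A third reply is that robustness does not rest on this analysis. That is correct. Method 2 includes treatment, method 3 assigns missing outcomes to success or failure, and SAP 3.3.1 asks how large an effect among the lost patients would change the main test. A modest attenuation in one supplementary result would be seen beside these.

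Two stronger readings are tempting and not supported. A reader might infer that the hot-deck imputation also ignores arm, but the ten-item list belongs to the regression version and no text excludes arm from the hot deck. A reader might also infer that the non-inferiority conclusion is compromised. Item 16 of the secondary analyses in SAP 3.2.2 does not say that it uses imputed data. If it did, the pull would favour non-inferiority, but at 10% missing a true 10-point difference would move by at most 0.10 × 10 = 1 point.

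**Conclusion.** The point holds for the regression-based multiple imputation as specified. Arm is in the analysis model and not in the imputation model, so the analysis is biased toward no difference. At the planned rates and 10% loss, the expected difference is 0.18 if the covariates carry none of the arm effect, with power about 0.74 instead of 0.81. It is 0.195 if they carry three quarters of it, and power is not visibly reduced when they carry most of it. The largest pull is 2 percentage points, a tenth of the effect. If loss reached 20%, which is an assumption, the floor would be 0.16.

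These figures rest on outcomes missing at random, on an assumed r, and on a simple Wald test in place of the SAP's random-intercept model with a permutation P-value. It would be wrong to infer that the trial's main conclusion is biased: the complete-case primary test does not use the imputation model. This is a correction to make before analysis, not a threat to the primary result.

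**What to change.** In SAP 3.5, add treatment arm to the prespecified covariates for the regression-based imputation, and state that it is forced into the model and not left to the cross-validated selection. Imputing separately within each arm would do equally well. Reword the one-line summary of method 1 so that it matches the detailed instructions. As a clarification only, state that arm is among the variables used by the hot-deck version.

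The cost is a line or two of SAP text. Treatment assignment is always known, so no new data are needed, and the primary analysis and sample size do not change.

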2.5. Definitions for primary endpoint

2.5.1. Determination of Treatment Success/Failure

Treatment success is defined as controlled ocular inflammation (see Table 2) in both eyes with 7.5 mg/day of prednisone, no periocular or intravitreal corticosteroid injections after the first 90 days of follow up, and ≤ 2 drops/day of topical 1% prednisolone acetate at the 6 month visit without treatment failure any point due to safety, tolerability or futility. Patients can stop medication at any time, but that in and of itself does not count as a treatment failure.

Table 2: Criteria for controlled inflammation

Parameter	Definition of control
Anterior chamber cells*	$\leq 0.5+$
Vitreous haze**	$\leq 0.5+$
Choroid & retina***	No active inflammation or retinal vasculitis posterior to the equator

*SUN criteria³⁰; ** NEI vitreous haze grading scale³¹ *** Cystoid macular edema is not sufficient to be called active inflammation

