3.2. Corticosteroid therapy

3.2.1. Oral prednisone

Prednisone vs. alternative oral corticosteroid

Unless contraindicated, oral prednisone should be used. An equivalent dose of an alternative oral corticosteroid may be used only if a specific contraindication to oral prednisone is present. All references to oral corticosteroid and specific dosing schedules presented in this Manual of Procedures are given for oral prednisone.

Initial dose

All patients enrolled in the study will be initially taking concomitant oral corticosteroids at 1 mg/kg or 60 mg daily, whichever is less. Treatment success is dependent upon successfully tapering concomitant prednisone to 7.5 mg/day. Initial corticosteroid dose will be continued for 2 to 4 weeks at which point prednisone will be gradually tapered.¹ Prednisone will be tapered to and held at 7.5 mg/day for the first 6 months of the study. Further reduction of corticosteroids will be allowed in Phase I after six months. If patients switch treatments and enter Phase II due to a failure of efficacy in Phase I, they will follow the same protocol as the initial Phase I corticosteroid

treatment and begin at 1 mg/kg or 60 mg, whichever is less. In patients failing for efficacy, investigators may start at a lower prednisone dose if they feel it is medically indicated. However, following the corticosteroid tapering guidelines is strongly encouraged. If patients switch treatments and enter Phase II due to a failure of intolerability in Phase I, then it is at the study doctor's discretion at what dose of corticosteroid to start the patient.

Tapering schedule

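### Supplementary missing-data method 2 models success at visits 1 to 6, but the prednisone taper makes months 1 and 2 near-structural failures; if visit is entered as a number, the month-6 result can be distorted

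*Combined protocol and SAP*

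**What the plan says.** SAP 3.5 lists four ways of handling loss to follow-up. Complete-case analysis is primary, and "All other analyses are to be considered supplementary". Method 2 is a longitudinal generalized linear mixed model, introduced as a regression "with visit as a covariate, and including a random effect for each person and for each eye within each person". Later in the same section the outcome is defined as the success of a person at a visit, with "covariates being site, country, treatment assignment, country-assignment interaction, visit (1:6), and visit-drug interaction (method 2 above". Variants are also to be reported, among them one that will "a) omit visit-drug interaction, and/or country assignment interaction".

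Protocol 2.5.1 defines success as "controlled ocular inflammation (see Table 2) in both eyes with 7.5 mg/day of prednisone", with limits on drops and injections, judged "at the 6 month visit without treatment failure any point due to safety, tolerability or futility".

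On steroids, protocol 3.2.1 starts patients at 1 mg/kg or 60 mg, whichever is less. It continues: "Initial corticosteroid dose will be continued for 2 to 4 weeks at which point prednisone will be gradually tapered". Table 6 then steps the dose down week by week to a hold at 7.5 mg.

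The SAP does not say whether visit is a factor or a number, how success is scored before month 6, or which contrast method 2 reports. It does mention the taper in 3.5, but only as a reason not to carry the last observation forward.

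**The concern.** The outcome contains a steroid-dose condition that the treatment schedule itself prevents most patients from meeting at the first monthly visits. A failure at month 1 or 2 then says little about the drug. A model that puts a straight line in visit through those zeros uses them to set the slope, and so the month-6 value. A model with separate visit terms tries to estimate log odds that are minus infinity.

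Method 2 is there to show that the treatment effect is robust to missing data, and SAP 3.5 itself advises caution in reading the complete-case result. A robustness check that can produce a month-6 difference where none exists, or whose printed treatment coefficient cannot be interpreted, does not serve that purpose.

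**Working it through.** **Taper against visit days.** Inputs are the initial hold of 2 to 4 weeks (protocol 3.2.1), the one-week steps at 50, 40, 35, 30, 25, 20, 17.5, 15, 12.5 and 10 mg (Table 6), and windows of ±15 days for months 1 to 5 (Table 9). I read visit (1:6) as the six monthly visits. Day 7.5 mg is reached = 7 × (hold weeks + number of later steps above 7.5 mg).

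| Start | Steps | Weeks | Day 7.5 mg is reached |
|---|---|---|---|
| 60 mg | 10 | 12–14 | 84–98 |
| 50 mg | 9 | 11–13 | 77–91 |
| 40 mg | 8 | 10–12 | 70–84 |
| 30 mg | 6 | 8–10 | 56–70 |

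With 365.25/12 days per month, month 1 is day 30 (window 15–45), month 2 is day 61 (46–76) and month 3 is day 91 (76–106). On schedule, a 50 or 60 mg start cannot succeed at month 1 or 2 and can begin to succeed at month 3. A 30 or 40 mg start can reach 7.5 mg before the month-2 window closes.

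The SAP's planning model for time to success (3.4.2: exponential, median 3.5 months for mycophenolate) does not reflect this. It implies 1 − 2^(−1/3.5) = 18% success by month 1 and 1 − 2^(−2/3.5) = 33% by month 2.

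**Sample size, used only to size the simulations.** SAP equation (5) gives 2N = 4 × (1.96 + 0.8416)² × 0.5 × 0.5 / 0.2² = 196.2, and 196.2/0.9 = 218.0, close to the stated 216. A two-proportion calculation gives 97 per arm, and 97/0.9 rounds up to 108 per arm, which is 216 exactly.

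**Simulation.** Random-intercept logistic data with 108 per arm, 10% dropout, no success at months 1 and 2, and person SD 1, 2 or 3. The month 3 to 5 rates and the SDs are assumptions. Site, country and eye terms were left out. Fits used maximum likelihood by quadrature (40 replicates per scenario) and R's glmer (12 replicates, SD 2).

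*Visit as a number, with interaction:* logit P = b0 + b1·arm + b2·visit + b3·arm·visit + u, so the month-6 contrast is b1 + 6·b3.
- glmer converged in 12 of 12 runs.
- True month-6 rates 40% and 60%: fitted 43–45% and 63–68% with a gradual rise, and 51–52% and 71–73% with an early plateau. The overshoot is about 3 to 13 points.
- The difference stayed at 0.20–0.23 against a true 0.20 when the arms rose alike.
- Arms equal at month 6 but different in speed: a false difference of 0.08–0.10. A separate simulation with 97 per arm and assumed month 3 to 5 rates of 20/45/50% against 5/20/35% gave 7.9 points (SD 5.7); a further run with 108 per arm gave about 9.
- Dropping months 1 and 2 but keeping visit numeric cut the overshoot only to about 0 to 6 points.

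*Visit as a factor, with interaction:*
- The month 1 and 2 coefficients ran to about −25 or beyond, and glmer gave warnings in 11 of 12 runs.
- The default treatment coefficient is the visit-1 contrast. Its standard error was 24 to 73, against at most 0.71 when only visits 3 to 6 were used.
- The month-6 log odds ratio was the same on visits 1–6 and 3–6: mean 1.45 in both, true value 1.34. The gap of 0.11 is within simulation error (0.49/√12 = 0.14). A cell with no successes is fitted with probability tending to zero and adds nothing to the likelihood.
- Factor coding on visits 3 to 6 left a bias of 0.2 points in the case where numeric coding gave about 9.

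*Interaction omitted, either coding:* the estimate is an effect pooled over visits, 0.15–0.18 where the true month-6 difference was 0.20.

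**The case against.** The strongest reply is that this is an unstated coding choice in one supplementary model. A reader might infer that method 2 must either fail to converge or give a distorted month-6 estimate. The documents do not support that: they leave the coding open, and under factor coding the month-6 contrast is sound despite the warnings. Nor do all warnings come from the early visits, since 6 of 12 fits on visits 3 to 6 alone also gave one. This objection stands and limits the claim.

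The false difference needs numeric coding and response curves that meet at month 6, and no document supplies such curves. That is fair as to size. A difference in speed is not far-fetched, though: time to control is a listed secondary objective (SAP 2.3.1).

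A reader might also take early success to be impossible. It is not. The starting dose depends on weight, protocol 2.3.2 accepts a lower start for tolerability, and 3.2.1 allows a faster taper for severe side effects. The documents do not give the share of such patients. Likewise, month 3 cannot be dismissed as uninformative, because its window (day 76–106) overlaps the days on which 7.5 mg is reached.

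Other safeguards exist. The imputation method uses prior inflammation grades and steroid dose, SAP 3.2.2 item 17 already models the grades at all time points, and 3.3.3 requires model checks. None of these states the coding or the reported contrast for method 2.

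On the random effect, SAP 3.1 does score eyes before combining them, so "including a random effect for each person and for each eye within each person" would suit an eye-level outcome. The outcome written for method 2 is one value per person, and an eye effect cannot be identified from that.

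**Conclusion.** The concern holds in a limited form. Months 1 and 2 are near-structural failures for patients starting at 50 or 60 mg, and method 2 as written makes no allowance for it. With numeric visit, month-6 arm rates are overstated by about 3 to 13 points, and a false difference of about 8 to 10 points can appear when the arms differ only in speed. When the arms rise alike, the difference is close to the truth. With factor visit, the printed treatment coefficient is uninterpretable but the month-6 contrast is not distorted. These sizes rest on assumed month 3 to 5 rates, assumed person SDs, zero success at months 1 and 2, and models without site or country terms.

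It would be wrong to conclude that the trial's main result is at risk: complete-case analysis is primary, and method 2 only supplements it.

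**What to change.** In SAP 3.5, respecify method 2 as follows:
- Fit it to months 3 to 6 with visit as a factor. Both parts are needed, because numeric visit on months 3 to 6 still misfits.
- State how success is scored at each of those visits, including for patients already declared a treatment failure.
- Report the month-6 arm contrast from the model with the visit-drug interaction, and label the no-interaction variant as an effect pooled over visits.
- Drop the eye-level random effect for the patient-level outcome.
- Name a penalised fit as the fallback if separation remains.

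The cost is SAP wording only. No data collection, sample size or primary analysis changes. Under factor coding, leaving out months 1 and 2 did not alter the month-6 estimate in the simulations, and starting at month 3 keeps the outcomes that can genuinely be successes.
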